Intergenerational transmission of sucralose and acesulfame-potassium from mothers
to their infants via human milk: a pharmacokinetic study

NCT05379270

DATE: April 9th, 2024

RESEARCH PROTOCOL

TITLE: Intergenerational Transmission of Low-calorie Sweeteners in Breast Milk

RESEARCH PLAN

A. Specific Aims

Aim 1: Determine the pharmacokinetics of sucralose and ace-K in mothers' breast milk and plasma after ingestion of a commercially-available diet beverage containing sucralose and ace-K.

Hypothesis 1: We hypothesize that ace-K will be rapidly transferred into breast milk, with peak concentrations measured within 1 hour of diet soda ingestion. We further hypothesize that sucralose will appear in the breast milk approximately 2 hours after ingestion, with peak concentrations detected approximately 8 hours later.

Aim 2: Assess the pharmacokinetics of sucralose and ace-K in exclusively breastfeeding infants following maternal ingestion of commercially-available diet beverage containing sucralose and ace-K.

Hypothesis 2: We hypothesize that sucralose and ace-K concentrations in infants' plasma will be proportional to concentrations measured in their mothers' breast milk.

B. Background and Significance

Low-calorie sweeteners (LCS), including sucralose and acesulfame-potassium (ace-K), provide sweetness without calories, and beverages with LCS are consumed by 44% of lactating women in the United States. The number of consumer products containing LCS has increased four-fold in recent years, and this trend will likely continue with ongoing public health efforts to reduce added sugars. Due to their chemical and physical properties, sucralose and ace-K are found widely in foods and beverages, often in combination. Yet, most consumers are unaware of their presence in a diverse array of products (e.g. non-diet fruit drinks, such as Hawaiian Punch™, no sugar added ice cream, "high-fiber" oatmeal, Carb Smart bread™) in addition to diet beverages. Neither sucralose nor ace-K are metabolized;³ and thus, both are detectable in biological fluids, including human breast milk. However, the current understanding of LCS effects on diet, weight, and health, especially when exposure begins early in life, is extremely limited.

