The study will take place in Clinical Research Unit (CRU) at Children's National Hospital and will last for approximately 9 hours, to provide sufficient time for baseline assessments and 8 hours of supervised sample collection following ingestion of a sucralose and ace-K containing diet beverage.

Written informed consent will be obtained at the start of the in-person visit, after which a brief medical history, and stage of lactation will be collected, and maternal height and weight will be measured. You will also be asked questions about other factors that may impact sucralose and ace-K pharmacokinetics, including smoking, alcohol intake, concomitant medications, and time since last feed will be collected. Infant anthropometric and birth data including length, weight, head circumference, birth order, sex, gestational age and the presence of any known health conditions will be collected via the mother's report. Mothers will also be asked to complete a questionnaire asking about the type of advice, if any, given to them about LCS use during lactation, as well as the amount and types of LCS-containing foods and beverages consumed since initiation of breastfeeding.

A breast milk sample (10 mL) will be collected from the mother for assessment of baseline sucralose and ace-K concentrations. The mother will then have an intravenous catheter (IV) placed by a trained phlebotomist in an antecubital vein, while in the recumbent position, after which, a baseline plasma sample (6 mL) will be collected.

After collection of a baseline plasma sample, mothers will be asked to drink 24 ounces of a commercially-available sucralose and ace-K sweetened diet beverage (hereafter diet beverage), containing a total of approximately 140 mg of sucralose and 85 mg of ace-K, within 10 minutes, prior to a standardized, LCS-free, breakfast meal consisting of a pre-packaged breakfast sandwich and fruit. These concentrations reflect the amount of sucralose and ace-K in two 12-ounce cans of a commercially-available, sucralose and ace-K sweetened diet soda, such as Diet Pepsi™ and corresponds to approximately 2

mg/kg sucralose and 1.15 mg/kg/day ace-K for a 70 kg adult, well below the acceptable daily intakes (ADI) 5 mg/kg and 15 mg/kg for sucralose and ace-K, respectively.

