After ingestion of the diet beverage, mothers will remain at the CRU for eight hours and will provide a plasma sample 0.5, 1, 1.5, 2, 3, 4, 6, 8 hours (6 mL at each timepoint) following diet beverage ingestion and a breast milk sample 1, 2, 3, 4, 6, 8, 12 hours following diet beverage ingestion (10 mL at each timepoint).

A plasma sample (100 μ L) will be collected from each infant at one of the following prespecified time intervals following maternal ingestion of the LCS containing beverage: 1.5-3 hours, 3-5 hours, 5-7 hours, 7-9 hours, and 9-14 hours. The infant sampling approach is designed to capture the timeframes when maternal breast milk concentrations for ace-K and sucralose will be at their maximum levels, while collecting only a single plasma sample from each infant to minimize risk. Infants' plasma will be collected via heel stick to reduce pain and minimize risk. Heel sticks are the most common way to collect infants' blood and are appropriate for most babies, including premature infants, neonates, and babies <6 months old. Heel sampling will be conducted by trained nursing staff in the CRU.

Breast milk samples will be immediately frozen at -20°C and transferred to a -80°C freezer at the end of each visit for long-term storage. Blood samples will be centrifuged at 4°C and the plasma stored at -80°C until analysis.

After collection of plasma and breast milk samples at the 8-hour timepoint (described above) mother-infant dyads will return home. The mother will be asked to collect the 12-hour breast milk sample at home and bring it to the hospital the following day. Additionally, the mother will be asked to complete a 3-day online, photo-assisted food record for the next three days and to continue to avoid products with LCS. The mother will be asked to return to the clinic between 7AM-9AM on these following three consecutive days (24, 48, and 72 hours after diet beverage ingestion) to provide a blood sample (6 mL each day) by a venous blood draw by a trained phlebotomist and to provide a breast milk sample (10 mL, 24-hour time point only). The total amount of blood collected from mothers over the course of the study (9-hour long study visit, and sample on three consecutive days) will be 72 mL. The total amount of breast milk collected from mothers over the course of the study (9-hour long study visit and 24-hour sample) will be 90 mL. The infant will provide a single blood sample, for a total of 100 μ L collected over the course of the study.

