4.3 Statistical Design and Power

Sample Size

Given that the primary purpose of the proposed study is to evaluate sucralose and ace-K pharmacokinetics, formal sample size calculations were not performed. In order to conservatively account for 20% attrition, we will recruit a total of 48 lactating women and their infants in order to complete measurements on a planned sample of 40 mother-infant dyads.

Planned Analyses

The concentration-time profile of sucralose and ace-K in plasma and breast milk from mothers will be analyzed by non-compartmental analysis (NCA)³⁵ and through a population pharmacokinetic approach using Pumas V1.0 (Baltimore, MD). Sucralose and ace-K concentrations (ng/mL) in plasma and breast milk will be first graphically explored and summarized descriptively. From the rich plasma and breast milk concentration-time data, NCA analysis will be performed to obtain the following PK parameters such as area under the curve (AUC), clearance, maximum concentration (C_{\max}), time-to-maximum concentration (T_{\max}) and terminal half-life ($T_{1/2}$).

The milk-to-plasma ratio (M:P) will be calculated for sucralose and ace-K. The population PK analysis of sucralose and ace-K in mothers from plasma and breast milk will be performed using the non-linear mixed effect modeling approach.³⁶⁻³⁸ Rich PK samples collected from mothers will be used to estimate the base PK model parameters and to characterize the effect of subject-specific prognostic factors (e.g., weight status, reported LCS consumption habits, overall dietary intake, body weight, maternal blood volume, age, sex, and race/ethnicity) to explain the between subject variability in the PK parameters. Plasma and breast-milk data will be analyzed together in the population PK analyses.

Using the sparse PK samples collected from the infants, a population PK analysis of sucralose and ace-K in infants will be performed, in combination with the robust maternal data.^{39, 40} The PK model in mothers will serve as the starting point for developing the pediatric PK model. Using principles of allometry, the PK parameters will be scaled down to infants using body weight and age maturation factors for the PK parameters.⁴¹

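### Milk is spot-sampled with no record, after the drink, of when the sampled breast was last emptied, so early ace-K milk values may be diluted by an unknown amount

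*Protocol*

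**What the plan says.** Protocol section D sets the baseline milk sample: "A breast milk sample (10 mL) will be collected from the mother for assessment of baseline sucralose and ace-K concentrations". After the drink it asks for "a breast milk sample 1, 2, 3, 4, 6, 8, 12 hours following diet beverage ingestion (10 mL at each timepoint", and on the next day the mother is to "provide a breast milk sample (10 mL, 24-hour time point only". The stated milk total is "9-hour long study visit and 24-hour sample) will be 90 mL".

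Among factors that may affect the pharmacokinetics, section D says "time since last feed will be collected". This is asked at the start of the in-person visit, and the text does not say from which breast. Section D does not describe a feed or expression at a set time before the drink, the breast to be sampled, or a record of feeds or pumping afterwards.

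Hypothesis 1 (section A) states that "ace-K will be rapidly transferred into breast milk, with peak concentrations measured within 1 hour of diet soda ingestion". SAP 4.3 then says: "From the rich plasma and breast milk concentration-time data, NCA analysis will be performed to obtain the following PK parameters", namely AUC, clearance, Cmax, Tmax and half-life. It also calls for M:P and fits milk jointly with plasma in the population model. Its example covariates do not include time since last feed or last emptying.

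**The concern.** A milk sample reflects what has collected in the breast since it was last emptied. If some of that milk was made before the drink, and it does not equilibrate quickly with plasma, the sample mixes milk without study sweetener and milk with it. The share of old milk is largest in the first samples and depends on each mother's feeding.

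These early samples matter most for the ace-K part of Hypothesis 1 and for early M:P. Non-compartmental analysis takes each milk value as it stands. The mothers are exclusively breastfeeding and stay for 8 hours, so feeds will probably occur between samples. If those times are not written down, they cannot be reliably reconstructed, and differences in breast filling may be read as differences in transfer.

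**Working it through.** **Reproducing the plan's figure.** One baseline sample, seven at 1-12 h and one at 24 h give (1 + 7 + 1) x 10 mL = 90 mL, which matches the Protocol. The study milk is therefore nine spot samples, and no full expression is kept.

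**Assumptions, none from the documents.** Milk is produced at a constant rate. Ace-K in newly secreted milk follows a one-compartment curve s(t), scaled to a peak of 1, peaking at 0.75 or 1 h with half-life 2, 3 or 4 h. The breast was last emptied tau hours before the drink and not again before the 1 h sample. Stored milk exchanges with plasma at rate k per hour.

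**Formula.** The concentration c(t) in the breast satisfies dc/dt = (k + 1/(tau + t)) x (s(t) - c), with c(0) = 0. With k = 0 this becomes c(t) = [integral of s from 0 to t] / (t + tau).

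**1 h value with no exchange.** Over the six curves, the integral of s from 0 to 1 h is 0.739 to 0.828. That is the 1 h value if the breast was emptied at the drink (tau = 0): 74-83% of the secreted peak. The ends of the range for tau = 1-3 h are:
- high: 0.828 / (1 + 1) = 0.41
- low: 0.739 / (1 + 3) = 0.18

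**1 h value as a percentage of the secreted peak, all six curves:**

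| Exchange k (per h) | Emptied at the drink | Last emptied 1-3 h before |
|---|---|---|
| 0 | 74-83 | 18-41 |
| 1 | 85-91 | 60-73 |
| 5 | 97-99 | 96-98 |

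**Early M:P.** Plasma is unaffected, so a paired 1 h ratio falls in step with the milk value. With k = 0 it is 1/(1 + tau) of the emptied value: 50% at tau = 1 h and 25% at tau = 3 h. With k = 1 it is about 70% (0.595/0.849) to 81% (0.735/0.912). SAP 4.3 does not say whether M:P comes from paired samples or from AUCs; these figures are for a paired ratio.

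**Between-mother spread with no exchange.** The share of the sample made after the drink is x = t/(t + tau). Take tau uniform on 0-3 h and t = 1 h:
- mean = (1/3) ln 4 = 0.462
- E[x^2] = (1/3)(1 - 1/4) = 0.25
- SD = sqrt(0.25 - 0.462^2) = 0.191
- CV = 0.191/0.462 = 41%

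At 2 h the mean is (2/3) ln 2.5 = 0.611 and the CV is 27%.

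**Effect of feeds during the visit.** Let full emptying feeds continue every 2, 2.5 or 3 h, with last emptying 1-2 h before the drink and k = 0. Tmax on the Protocol's grid is then 1-3 h and Cmax is 61-99% of the secreted peak. The 1 h value is still 25-41% in four of the six schedules (62-73% with k = 1). In the other two, a feed falls at the drink or half an hour after it.

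**Second model as a check.** Here a residual volume of 30-150 mL is present at the drink. Milk is made at 30 mL/h, 10 mL is removed at each sample, and feeds come about every 2.5-3 h. Two oral plasma curves are used (ka/ke 2/0.35 and 4/0.5 per h). Results are relative to an emptied breast, for which Tmax is 1-2 h:

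| k (per h) | Tmax (h) | Cmax (% of emptied value) |
|---|---|---|
| 0 | 2-4 | 36-77 |
| 0.5-1 | 1-3 | 64-95 |
| 2 | unchanged | 87-99 |
| 5 | unchanged | 98-100 |

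With residual volume varied over 10-120 mL and nothing else varying (first plasma curve), the CV of the 1 h value is 38% at k = 0, 7% at k = 1 and about 0% at k = 5. In no scenario did residual milk raise Cmax or bring Tmax forward.

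**The case against.** The strongest objection is that the size rests on quantities the documents do not give. If stored milk equilibrates quickly with plasma, a spot sample is close to a point concentration and there is almost nothing to correct. This stands, and it is why the effect is stated as a range that reaches nearly nil.

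A reader might infer that ace-K milk Tmax will be pushed to 3-6 h and Cmax cut to 39-64% of the secreted peak. Those figures need zero exchange and no feed before the sample. The 6 h case, with last emptying 3 h before the drink, means 9 h without a feed in an exclusively breastfed infant. The documents do not support that.

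A reader might also infer that the breasts will be full at the drink. The Protocol is silent: a feed shortly beforehand is neither required nor excluded.

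The plan does recognise the factor, since it asks time since last feed, and the SAP's covariate list is given as examples, so using it is not ruled out. But one answer before the drink cannot describe the breast at later samples. The structure of the joint population model is not stated either, so only the non-compartmental analysis can be said to take milk values as they stand.

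Controlling emptying would not rescue Hypothesis 1. The first milk sample after the drink is at 1 h, so an earlier peak cannot be seen in any case. That is a separate limit.

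Finally, a nursing infant also swallows mixed milk. The concern is with milk-transfer pharmacokinetics; bias in infant exposure does not follow.

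**Conclusion.** The concern holds as a possible bias of known direction and unknown size. Sampling is by 10 mL spot samples, with no control or later record of when the sampled breast was last emptied. Early ace-K values and early M:P may be too low, Tmax may be late, and between-mother variability may be inflated.

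The range for the 1 h sample runs from a two- to four-fold reduction relative to an emptied breast (no exchange, last emptied 1-3 h before) to almost none (exchange of 5 per h). Effects on Cmax and Tmax are smaller once feeds during the visit are allowed for. All sizes depend on assumed secretion curves, feeding times and exchange rates. The case for acting is that the missing information is cheap to collect at the time and cannot be reliably recovered afterwards.

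**What to change.** **Protocol section D, milk sampling.** Take the scheduled samples from one named breast. For every milk sample, including those at 12 and 24 h, record the clock time that breast was last fed from or pumped. Log all feeds and pumping during the visit.

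**SAP 4.3.** Add time since last emptying to the joint milk-plasma model as a component to be tested. Compare a point-concentration model with one that allows accumulation since the last emptying, with exchange estimated or varied. Averaging over the interval should not be imposed, because it builds in zero exchange and would be misspecified if stored milk equilibrates. Report milk Cmax, Tmax and early M:P with this sensitivity analysis.

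**Optional.** A feed or expression at a set time before the drink would reduce the problem at source. It should be adopted only if reconciled with infant feeding and the heel-stick schedule, since it could shift the infant's next feed and so affect Aim 2.

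**Cost.** A feed log, one extra field per milk sample and a little more modelling.

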Additional infants' covariates will be evaluated in the combined PK model. The final population PK model for sucralose and ace-K in both mothers and infants will be evaluated and qualified using standard goodness of fit diagnostics and quantitative predictive check methods. The relative infant dose (RID) of sucralose and ace-K will be calculated as described in the FDA lactation guidance.⁴² Given that blood volume differs in obese vs. lean individuals, adjustments for blood volume will be performed by calculating the total mass of sucralose or acesulfame-potassium in breast milk, as in our prior study.⁷

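### The supplied text describes no record of infant feeds between the mother's drink and the single heel stick, so the infant PK model and Hypothesis 2 would rest on assumed feed times, mainly in the early windows

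*Protocol*

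**What the plan says.** Protocol Section D takes a single heel-stick sample from each infant, which "will be collected from each infant at one of the following prespecified time intervals following maternal ingestion of the LCS containing beverage": 1.5-3, 3-5, 5-7, 7-9 or 9-14 h. The clock starts at the mother's drink.

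The only feed-related item is in the list of questions at the start of the in-person visit, before the baseline samples and the drink: "smoking, alcohol intake, concomitant medications, and time since last feed will be collected". It does not say whether the feed is the infant's or the mother's. The infant data listed are body measurements, birth data and known health conditions. The food records are completed by the mother, and infant feeds are not mentioned.

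SAP section 4.3 plans an infant population PK analysis from these sparse samples together with the maternal data. "The PK model in mothers will serve as the starting point for developing the pediatric PK model", and "the PK parameters will be scaled down to infants using body weight and age maturation factors for the PK parameters". It adds: "Additional infants' covariates will be evaluated in the combined PK model". It does not say which feed times or milk volumes form the infant's dose input.

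Protocol Section A expects that "ace-K will be rapidly transferred into breast milk, with peak concentrations measured within 1 hour of diet soda ingestion" and that "sucralose will appear in the breast milk approximately 2 hours after ingestion". Hypothesis 2 is that infant plasma concentrations are proportional to those in the mother's milk.

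**The concern.** An infant's exposure depends on when it fed, what the milk contained at that moment, and how much it took. Time since the mother's drink fixes none of these. With one sample per infant, a low value could mean that the infant had not yet fed, that it fed before the sweetener reached the milk, that the feed was small, or that clearance is fast. The first two are matters of timing. If feed times are not written down on the day, analysis cannot recover them later.

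Aim 2 and Hypothesis 2 depend on these single values. The milk concentration relevant to Hypothesis 2 is that of the feeds actually taken, and it cannot be identified without feed times. The first infant window opens at 1.5 h, before sucralose is expected in milk at all.

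**Working it through.** The plan states no figure on this point, so there is none to reproduce. The question is how many infants could be sampled before they had been dosed.

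**Inputs.** From the protocol: the sampling windows (Section D) and sucralose appearing in milk at about 2 h (Section A). Assumed: regular feeds every T = 2, 3 or 4 h, random phase relative to the drink, and heel sticks spread evenly within each window.

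**Formula.** For a heel stick at time t, let L be the time from which a feed counts: L = 0 for any feed since the drink, L = 2 h for a feed since sucralose is expected in milk. The chance of no such feed is 1 if t < L, and otherwise max(0, 1 - (t - L)/T). The window figure is the average over the window.

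**Worked cases.**
- L = 0, 1.5-3 h, T = 3: the integral of 1 - t/3 from 1.5 to 3 is 1.5 - 1.125 = 0.375; divided by 1.5, 25.0%.
- L = 2, 1.5-3 h, T = 3: 0.5 h at probability 1, plus 1 h at average 1 - 1/6 = 0.833, gives 1.333; divided by 1.5, 88.9%.

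| Window | No feed since drink (T = 2, 3, 4 h) | No feed since sucralose expected in milk (T = 2, 3, 4 h) |
|---|---|---|
| 1.5-3 h | 4.2%, 25.0%, 43.8% | 83.3%, 88.9%, 91.7% |
| 3-5 h | 0%, 0%, 6.3% | 12.5%, 33.3%, 50.0% |
| 5-7 h | 0%, 0%, 0% | 0%, 0%, 6.3% |
| 7-9 h | 0%, 0%, 0% | 0%, 0%, 0% |

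The SAP plans 40 completing dyads. If they were split evenly over five windows (an assumption; the allocation is not stated), each window has 8 infants. In the first, 0.83 x 8 = 6.7 to 0.92 x 8 = 7.3, about 7 of 8, would have had no feed since sucralose was expected in milk.

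**Infants already dosed.** An ace-K illustration shows how the effect fades. It simulates one-compartment infants with the same milk curve, hourly intake and clearance, so that only feed timing differs. Assumed: feed interval uniform on 2-4 h, random phase, volume proportional to interval, no ace-K in milk before the drink, infant half-life 2, 4 or 8 h, absorption 0.7, 1.5 or 3 per h, milk peak at 0.8-1.0 h, and milk decline 0.2 or 0.35 per h. The ratio of the 90th to the 10th percentile of infant plasma is 1.6-2.6 at 4 h and 1.1-1.6 at 11.5 h. I give no such range for sucralose, because it depends on a milk-curve shape that the documents do not state.

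**What feed times cannot settle.** In a linear model, concentration depends on dose divided by CL/F and V/F. If every assumed intake is multiplied by 1.25 and CL/F and V/F are also multiplied by 1.25, the predicted concentrations are identical. An intake assumed 25% too high therefore gives infant CL/F and V/F 25% too high with the same fit, unless the scaled maternal values hold them in place.

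**The case against.** **The two sweeteners carry some timing information.** Both are drunk together, and mothers avoid low-calorie sweeteners for the preceding week. An infant with ace-K present and sucralose absent has probably fed since the drink; one with neither probably has not. From the table, infants in the 1.5-3 h window who have fed, but not since sucralose was expected in milk, make up 83.3 - 4.2 = 79%, 88.9 - 25.0 = 64% or 91.7 - 43.8 = 48%. This stands. A reader might infer that an unfed infant and one fed too early can be told apart only from feed times; that is too strong. Still, the pattern is blurred by assay limits, residual exposure and very early feeds, and it gives neither the time nor the number of feeds.

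**The model does not start from nothing.** The maternal model and the allometric scaling inform infant clearance and volume, so a reader who inferred that the infant model cannot be fitted, or that Aim 2 fails, would go beyond the documents. Scaling does not, however, say when or whether an infant was dosed.

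**Feeds may be recorded elsewhere.** The SAP text before section 4.3 was not supplied, and study forms may include a feed log. The team lists time since the last feed among factors that may affect the kinetics, so it regards feed timing as relevant. The absence can therefore be asserted only for the supplied text. Even so, the protocol's data-collection section lists the infant data in detail without it.

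**Relative infant dose.** The SAP says "The relative infant dose (RID) of sucralose and ace-K will be calculated as described in the FDA lactation guidance". That source may supply a standard intake, so no gap in the relative infant dose should be inferred. It does not tell the reader what feed times the infant model will use.

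**Conclusion.** The point holds, limited to the supplied text and to the interval between drink and heel stick. Followed as written, the plan leaves the infant population PK model and Hypothesis 2 without the times at which each infant was dosed. The weight falls on the 1.5-3 h window for both sweeteners and on the 3-5 h window for sucralose. By 5-7 h at most 6% would lack a feed since sucralose was expected in milk, and by 7-9 h none would.

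The shares rest on assumed regular feeds every 2 to 4 h at random phase and on the protocol's approximate 2 h for sucralose. They indicate size and do not predict this cohort. The early samples are not worthless: they remain informative once it is known whether and when the infant fed. The plan should be changed because the information is cheap to record and cannot be recovered afterwards. My confidence is medium, because part of the SAP and the study forms were not available.

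**What to change.** **Protocol Section D.** Log the start and stop time of every infant feed from the drink to the heel stick, by staff in the unit and by the mother after discharge, together with the exact heel-stick time. If a study form already does this, cite it. Clarify whose feed the start-of-visit question refers to.

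**SAP section 4.3.**
- Enter each logged feed as a dose event in the combined population PK model. Use the milk concentration predicted at the feed time by the joint maternal plasma-milk model. This is preferable to straight-line interpolation, because no milk sample lies between baseline and 1 h, where the ace-K peak is expected.
- State the intake volume assumed per feed, with a sensitivity range.
- Keep infants with no feed after the drink in the model, with zero post-drink dose, and list them.
- Assess Hypothesis 2 through this model.
- State that infant clearance remains conditional on the intake assumption, because volumes are not measured.

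**Cost.** A one-page log, a few lines in the SAP, and a few minutes of staff and mother time, with no invasive procedure. Times logged at home after the 8-hour discharge will be less precise, which affects heel sticks after that point. Logging times alone removes the uncertainty about when, and whether, the infant was dosed; it does not separate intake from clearance.
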